10.5 Recording of Data and Retention of Documents

Confidentiality of subject records must be maintained to ensure adherence to applicable local privacy regulations.

The Investigator must retain essential documents for a period of time specified by local law or per the Investigator's Clinical Trial Agreement after the completion of the study, whichever is longer, unless otherwise notified by the Sponsor. The Investigator agrees to adhere to the document retention procedures when signing the protocol Investigator Statement of Approval.

Essential documents include but are not limited to the following:

- IRB approvals for the study protocol, all amendments, ICF(s), and advertisements
- IRB annual study review (if requested)
- IRB correspondence and reports (e.g., AE/UADE reports, protocol deviations, and safety updates)
- Regulatory documents (e.g., financial disclosure and delegation of authority forms)
- All source documents
- Archive of eCRFs
- Subject's signed ICF
- Investigator Clinical Trial Agreement
- Accountability records for the test article(s)
- Correspondence from and to the Sponsor

• Any other documents relevant to the conduct of the study

In the event that the Investigator withdraws from the study (e.g., retirement, relocation), study records will be transferred to a designee (e.g., another Investigator, and/or site IRB) mutually agreed upon by Investigator and Bausch + Lomb. The Investigator will provide notice of such transfer in writing to Bausch + Lomb.

10.6 Auditing Procedures

Audits of clinical research activities in accordance with the Sponsor's internal Standard Operating Procedures to evaluate compliance with the principles of GCP may take place. A regulatory authority may also wish to conduct an inspection (during the study or after its completion). If an inspection is requested by a regulatory authority and/or IRB, the Investigator must inform the Sponsor immediately that this request has been made.

10.7 Institutional Review Board

The Investigator should ensure, in accordance with 21 CFR 56, that their participation in the study, in addition to the protocol, subject recruitment materials (written information or materials including web pages, radio advertisements, television spots or written text developed to encourage subject enrollment) and the ICF to be used in this study are approved by their institution IRB, or if not using their institution's IRB, approved by the reviewing central IRB prior to entering any subjects in the study.

Documentation of IRB approval of the study protocol and informed consent must be provided to the Sponsor prior to initiation of the study. In addition to approving the 'Investigational Protocol' and 'Informed Consent' documents, a statement of IRB Approval should also contain the name(s) of approved Investigators, and the signature of the IRB Chairperson. The Investigator must ensure that the reviewing IRB has provided approval for any protocol amendments prior to implementation. If the amendment necessitates a revision to the ICF, the Investigator should ensure the revised form is also submitted to and approved by the Sponsor and the IRB prior to implementation.

10.8 Publication of Results

All study data generated as a result of this study will be regarded as confidential, until appropriate analysis and review by the Sponsor or its designee and the Investigator(s) are completed. The results of the study may be published or presented by the Investigator(s) after the review by, and in consultation and agreement with the Sponsor, and such that confidential or proprietary information is not disclosed.

Prior to publication or presentation, a copy of the final text should be forwarded by the Investigator(s) to the Sponsor or its designee, for comment. Such comments shall aim to ensure the scientific integrity of the proposed publications and/or presentations and ensure

that the data and material referring to Technolas Perfect Vision GmbH products and activities receive fair, accurate, and reasonable presentation.

Appendix A. Schedule of Visits and Parameters

All study tasks must be performed by qualified study site personnel as indicated on the delegation of authority log under the supervision of the Principal Investigator.

Test	Visit 1 Pre-Op (Day-60	Visit 2 Operative Visit (Day 0)	Visit 3 Day 1 ¹	Visit 4 Week 1 (Day 5-	Visit 5 Month 1 (Week 3-	Visit 6 Month 3 (Week	Visit 7 Month 6 (Week	Visit 8 Month 9 (Week
	to Day -1)	(Day 0)		9)	5)	10-14)	21-26)	35-43)
Informed Consent/HIPAA	X							
Eligibility	X	Х						
PROWL Questionnaire ²	X					X	X	X
Adverse Events	X	X	Х	X	X	X	X	X
Complications		X	Х	X	X	X	X	X
Subject Demographics	X							
Medical/Ocular History	X							
Concomitant Medications	X	X	X	X	X	X	X	X
Schirmer's Test ³	X						X	
LASIK Surgery, Intraoperative Events ⁴		X						
Manifest Refraction	X			X	X	X	X	X
Keratometry ⁵	X							
Endothelial Cell Density (ECD) ⁶	X						X	
Corneal Topography	X				X	X	X	X
Pupil Size ⁷	X					X	X	X
UCNVA ⁹	X		X	X	X	X	X	X
UDVA ⁸	X		X	X	X	X	X	X

¹ The same parameters are to be measured at each examination performed until re-epithelialization occurs (when applicable).

² The PROWL questionnaires ^{34, 35} should be completed by the study subject in a secluded area, free of directions from clinical staff. at Visit 6, 7 and 8.

³ The Schirmer's test must not be conducted with anesthesia.

⁴ LASIK surgery is to be conducted by a refractive surgeon adequately trained by B+L or TPV technical representatives for use of the TENEO 317 laser system and supervised by a technical representative for at least the first 4 LASIK surgeries completed by the refractive surgeon.

⁵ Keratometry should be assessed only at the pre-operative study visit and as needed at a post-operative study visit to assess anomalous results in the post-operative period. Pachymetry should take place after manifest refraction has been done to avoid disturbing the cornea.

⁶ Preoperative and 6 Months ECD measurements will be done at three or four clinical sites by specular microscopy.

⁷ Pupil size should be assessed under mesopic conditions at the pre-operative study visit and at months 3, 6 and 9 as well as Unscheduled Visits

⁸ UCNVA, UDVA and BSCVA measurements are to be taken under photopic conditions (approximately 85 cd/m²) for each eye monocularly.

	Visit 1	Visit 2		Visit 4	Visit 5	Visit 6	Visit 7	Visit 8
Test	Pre-Op (Day-60 to Day -1)	Operative Visit (Day 0)	Visit 3 Day 1 ¹	Week 1 (Day 5- 9)	Month 1 (Week 3- 5)	Month 3 (Week 10-14)	Month 6 (Week 21-26)	Month 9 (Week 35-43)
Distance BSCVA ⁹	X			X 9	X 10	X 10, 10	X 10,11	X 10,11
Contrast Sensitivity	X						X	
Slit Lamp Examination ¹¹	X		X	X	X	X	X	X
Pachymetry ¹²	X							
Cycloplegic Refraction	X							
Intraocular Pressure ¹³	X				X	X	X	X
Dilated Fundoscopic Exam	X					X ¹⁴	X ¹⁴	X ¹⁴

⁹ If the visual acuity with spectacle correction is ≥ 2 lines (10 letters) below that obtained at Visit 1, a rigid contact lens over refraction should be performed to estimate the best possible corrected visual acuity.

¹⁰ BSCVA to be completed OD and OS.

¹¹ The slit lamp examination should include a complete survey of the anterior segment and grading of findings as detailed in Appendix B.

¹² Pachymetry should be assessed only at the pre-operative study visit and as needed at post-operative study Visit 7 to assess anomalous results in the post-operative period. Pachymetry should take place after manifest refraction has been done in order to avoid disturbing the cornea.

¹³ Intraocular pressure should preferably be obtained using Goldmann applanation tonometry.

¹⁴ Dilated fundus examination (only required if loss of BSCVA occurs compared to pre-op BSCVA).

Appendix B. Description of the Investigative Device and Methods of Clinical Evaluation

1.0 TENEO 317 MODEL 2 EXCIMER LASER DESCRIPTION

The Teneo 317 Model 2 excimer laser consists of the following system components:

1.1 Excimer Laser Head:

The laser head provides the following output characteristics:

Laser medium:	ArF
Laser wavelength:	193 nm
Gas mixture:	Argon / Fluorine / Neon
Operating fill pressure:	6 bar
Repetition rate:	500 Hz
Power:	< 10.000 mW
Pulse width (duration):	8 ± 3 ns
Emergent beam size (VxH):	6 x 3 mm
Beam divergence (VxH):	51 x 27 mrad
Fluence on cornea:	200 mJ/cm^2

1.2 Laser Gas System

Included in the laser system is a gas bottle of the laser gas mixture with Argon, Fluorine and Neon. Additionally, there is another gas bottle containing Nitrogen gas, which is used for flushing the beam path and gas system for installation and service and an ongoing gas exchange inside the sealed beam path. Components of the gas system include automatic valve, pressure reducer, pressure sensors (high/low pressure section), vacuum pump, fluorine filter, computer-controlled gas delivery.

1.3 System Control

Computer and software

A computer and proprietary software are used to coordinate the control of the system, as well as determine the ablation profile and algorithm for each subject eye to be treated.

I/O (Input/Output) Board and Scanner Drivers

The I/O (Input/Output) Board receives and sends signals to the computer, as well as controlling components of the system, such as turning on and off the laser radiation, opening and closing the shutter. Furthermore, the energy delivered to the eye is monitored.

1.4 Laser Beam Delivery System

The laser beam delivery system consists of aperture, two safety shutters, focusing lens, galvanometers with scanning mirrors, and two 45°-deflection mirrors. The main functions of the beam delivery system are to shape the laser beam to the proper size and beam profile, and direct the laser pulses by the scanner to the locations on the eye determined by the computer and software.

1.5 Subject and Doctor Interface

The laser system components that comprise the subject-doctor interface include the patient bed with a joystick, operating microscope with a centration reticule, illumination light, diode-laser for fixation light, diode-laser for focus and aiming light, plume evacuator, footswitch for shutter / laser-control, computer keyboard, touchscreen, laser emission indicator, key-switch (on/off) and emergency stop, USB ports for user key and USB storage device.

1.6 System Integration

The mechanical integrity of the system is provided by a welded metal frame, with metal plates bolted to the frame. All components and sub-components are fastened to the plates and the frame. The housing of the system is used to protect the users and subjects from electric and radiation hazards. Access is only possible by using a special tool to open the covers. The electronic components are connected with shielded cable. Isolation transformers and line filters are used for the electric power lines.

1.7 Power Stability

The power stability unit consists of a closed-loop energy check system that verifies pulse energy at different control points along the sealed beam path, adjusting pulse energy throughout the treatment and maintaining consistent laser energy output from the laser head.

1.8 Electrical Safety

The Teneo 317 Model 2 excimer laser system is designed to meet the ISO/IEC standard 60601-1 (Edition 3.1): Medical Electrical Equipment – Part 1: General Requirements for Basic Safety and Essential Performance.

1.9 Radiation Disabling

Laser radiation is prevented from exiting the laser system in certain situations, such as in the following cases:

(1) The physician detects a non-optimal event, i.e., eye movement, and releases the footswitch,

- (2) The Eye tracker detects eye movements out of predefined ranges,
- (3) The plume evacuator failure is detected,
- (4) When the energy is out of the expected range,
- (5) When the surgery is completed,

- (6) When the Emergency stop button is pushed, and
- (7) an optional remote interlock is activated.

The shutter has been tested to be able to block the laser radiation in <50 msec. In addition, there are two shutter position sensors, one for the "open" and another for the "closed" position. If the computer receives an incorrect position signal, the laser head is shut down.

1.10 Eye Tracking

The TENEO 317 eye tracker (ET) is essentially the same as the approved 217z ET module, as both systems perform real-time (dynamic) adjustments to laser pulse positioning in response to intraprocedure eye movements. The ET for the TENEO 317 was updated to accommodate the faster repetition rate of the 317 laser (laser frequency TENEO 317: 500Hz vs. 217z: Hz100Hz; ET frequency TENEO 317: 1.740Hz vs. 217z: 240Hz), otherwise the following description applies to both ET modules.

The lateral (X/Y) eye tracker (ET) uses a co-axial infrared camera to follow movements of the pupil in order to provide positioning information to the laser system. The eye tracking system scans the image and determines the location of the center of gravity of the pupil. The center of the pupil is provided as a feedback to the computer which corrects the laser beam position to match the detected pupil center position. Should the cornea leave the predefined interval in X/Y, the laser system stops the application of pulses until the cornea is repositioned inside the acceptance range.

A second rotational/Z camera, tilted 12° to the optical axis, detects the changing angle for torsional tracking. The computer corrects the laser beam position via the scanning system to match the calculated position. Should the cornea exceed a predefined angle, the laser stops the application of pulses until the cornea rotation angle is within the accepted range.

Lastly, the ET utilizes a passive Z-tracking feature which uses information from both camera systems (X/Y) and torsional tracker to determine the position of the cornea in the axial (Z-direction) direction based on triangulation. Should the cornea leave the predefined interval in Z, the laser system stops the application of pulses until the cornea is repositioned within the accepted range.

1.11 Plume Evacuator

The Teneo 317 Model 2 excimer laser integrated plume evacuator system removes debris from a region above the surgical field and avoids the distribution of the debris into the surgery room during the ablation process. It is placed close to the ablation level to evacuate plume as effectively as possible through an integrated nozzle. If the suction nozzle is not in the treatment position, or suction flow fails during treatment the laser stops the application of pulses until the fault condition is resolved.

1.12 Slit Lamp

An optional slit lamp is integrated in the system. The slit can be adapted in width and position to be able to examine the patient's eye after flap repositioning after the excimer laser procedure has been completed.

2.0 CREATION OF THE CORNEAL FLAP FOR LASIK

The creation of the required corneal flap will be performed with a femtosecond laser. Any commercially approved femtosecond laser can be used to create the corneal flap prior to LASIK treatment.

3.0 THE PATIENT-REPORTED OUTCOMES WITH LASIK (PROWL) QUESTIONNAIRE

All subjects will complete the PROWL-PRQ Questionnaire ³⁴ pre-operatively and all enrolled subjects will complete a separate post-operative PROWL-POQ Questionnaire ³⁵ at several post-operative study visits. Note the entire PROWL questionnaire will be administered, mean values by question and by treatment group will be summarized, and only specific questions relating to specific patient-centric domains described in Section 5.2.3, Section 8.5, and/or Section 9.6.3.3.1 will be scored and analyzed. Questionnaires will be completed independently by subjects in a private space at the beginning of each applicable visit, prior to other study assessments being performed. The PROWL-PRQ Questionnaire will be given once, at the pre-operative screening visit (Day -60 to Day -1), and the PROWL-POQ Questionnaire will be given at every study visit beginning with Visit 6 (3 months, Week 10-14) until the subject exits the study.

Subjects should be instructed to complete as many of the questions as possible by checking one box associated with each question, with an estimated completion time for each Questionnaire of about 30 minutes. Subjects will be asked to read each question carefully and answer as appropriate for how they feel – there are no right or wrong answers. Subjects will be told the test coordinator will not be present during the completion of the Questionnaire and cannot provide any guidance on how to answer any questions. If a subject is not sure of an answer, they should be encouraged to guess at an answer that seems right to them. When done, the test should be given to the study coordinator.

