	14	8	Mainly vision Mainly other reason Both vision and other reasons No scoring needed
Driving	15-17	9-11	No difficulty = 100 A little difficulty = 75 Moderate difficulty = 50 Extreme difficulty = 25 Never drive during the daytime because of vision, or Never drive at night because of vision or Never drive in these conditions because of vision = 0 Never drive during the daytime for other reasons, or Never drive at night for other reasons, or Never drive in these conditions for other reasons = N/A
	18	12	No difficulty at all =100 A little difficulty = 200/3 Moderate difficulty = 100/3 A lot of difficulty = 0
	Domain score questions ans		es of scores of all questions)/(total number of

	Note: Questions with answers as N/A will be treated as not answered and excluded from the calculation. Questions PRQ12, 13, 14 (or POQ6, 7, 8) are excluded from the domain score calculation.		
	34, 35, 36	28, 29, 30	Yes = 0 No = 100
Vision Clarity	34a, 35a, 36a	28a, 29a, 30a	Very = 0 Somewhat = 25 A little = 50 Not at all = 75
Vision Clarity	Domain score = (sum of scores of all questions within the domain)/(total number of questions answered) Note: When 34 is No, 34A should not be answered. However, in case 34 is No and 34A is answered, ignore 34 result from the domain score calculation and only use 34a result. Apply the same rule when the discrepancy happens to 35 (35A), or 36 (36A), or 28 (28A), or 29 (29A), or 30 (30A).		

 Table 5. PROWL Question Categories and Questions to be Analyzed

Topics - Table Summary with Descriptive Statistics	PROWL-PRQ Questions	PROWL-POQ Questions
Vision Satisfaction	37	34
Vision Clarity	5	5
Satisfaction with LASIK Surgery		71-78

Table 6a. Normalization Scores for PROWL Questions in Table 4

Topics - Table Summary with Descriptive Statistics	PROWL-PRQ Questions	PROWL-POQ Questions	Normalized Score
Vision Satisfaction	37	34	Completely satisfied = 100 Very satisfied = 80 Somewhat satisfied = 60 Somewhat dissatisfied = 40 Very dissatisfied = 20 Completely dissatisfied = 0
Vision Clarity	5	5	Perfectly clear = 100 Pretty clear = $200/3$ Somewhat clear = $100/3$ Not clear at all = 0
Satisfaction with LASIK Surgery		71-78	Scoring of each of these questions should be provided as percentages for each possible response.

Statistical Analysis Plan Version 1.0 / Protocol Number: 884

	Example 1) POQ72:
	Currently, how satisfied or
	dissatisfied are you with
	how long it took to see
	improvement in your vision
	after LASIK surgery?

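### SAP 6.5.8.9 drops a Vision Clarity 'No' (100) when its follow-up is also ticked, so 'No' plus 'Not at all' scores 75

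*Protocol*

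**What the plan says.** Protocol Appendix B 3.0 sets out how PROWL is completed. "Subjects should be instructed to complete as many of the questions as possible by checking one box associated with each question" is the general instruction. For doubtful items it adds: "If a subject is not sure of an answer, they should be encouraged to guess at an answer that seems right to them". Subjects are also told to read carefully and answer as appropriate, and that the coordinator cannot guide them. Nothing is said about follow-up items that apply only after a particular lead answer.

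SAP 6.5.8.9 scores Vision Clarity from three pairs of items: PRQ 34/34a, 35/35a and 36/36a before surgery, and POQ 28/28a, 29/29a and 30/30a afterwards. The lead item scores 0 for 'Yes' and 100 for 'No'. The follow-up scores are "Very = 0 Somewhat = 25 A little = 50 Not at all = 75". The domain score is the sum of item scores divided by the number of questions answered.

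A note covers the case where a 'No' is accompanied by a follow-up answer. It starts from "When 34 is No, 34A should not be answered" and then rules: "in case 34 is No and 34A is answered, ignore 34 result from the domain score calculation and only use 34a result". The same rule is extended to the other pairs on both questionnaires. The domain is summarised descriptively by visit and as change from baseline.

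**The concern.** The note treats every 'No' with a completed follow-up as a discrepancy and always resolves it in favour of the follow-up. 'No' with 'Not at all' does not look like a contradiction, since both answers point to the best state. Yet the pair gets 75, and the same 'No' with the follow-up blank gets 100. Once any follow-up box is ticked, 100 is out of reach.

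The steps 0, 25, 50, 75 and 100 look like a single five-step scale with 'No' at the top, in which 75 is meant for someone who answered 'Yes' but was not bothered. In the Subject Symptoms row of the same table the SAP says best health should score 100; the Vision Clarity note departs from that idea. SAP 6.6 lists the changes to the questionnaire analysis but gives no reason for the override.

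At stake is the meaning of the Vision Clarity mean and its change from baseline. Both would partly reflect how subjects fill in the form.

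**Working it through.** The documents give no worked Vision Clarity score, so there is no figure to reproduce. The check applies the printed scoring.

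**Inputs (SAP 6.5.8.9).** Lead item: 'Yes' = 0, 'No' = 100. Follow-up: 0, 25, 50 or 75. Domain score = sum of scores / number of questions answered. I take an ignored lead answer to leave both the sum and the count, and a blank follow-up to be unanswered.

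**One pair with lead answer 'No'.**

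| Follow-up | Score under the SAP note |
|---|---|
| blank | 100 |
| 'Not at all' | 75 |
| 'A little' | 50 |
| 'Somewhat' | 25 |
| 'Very' | 0 |

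A stray 'Not at all' costs 100 − 75 = 25 points on that pair.

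**Domain score with 'No' to all three lead items.**

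| Stray 'Not at all' ticks | Calculation | Score |
|---|---|---|
| 0 | (100 + 100 + 100)/3 | 100 |
| 1 | (75 + 100 + 100)/3 | 91.67 |
| 2 | (75 + 75 + 100)/3 | 83.33 |
| 3 | (75 + 75 + 75)/3 | 75 |

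If the 'No' were kept, all four rows would be 100. A subject answering 'No' throughout who ticks the three follow-ups at one visit only shows a false change of 25 points; its sign depends on which visit.

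**Effect on a mean.** Let p be the share of lead items answered 'No' at a visit, and f the share of those carrying a stray 'Not at all'. The item mean at that visit, with each pair counted as one score, falls by

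25 × f × p.

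The error in change from baseline is

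−25 × (f_post × p_post − f_pre × p_pre).

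The documents give neither f nor p. As an assumption, hold f constant and let p rise from 20% to 80%. The error is then −25 × f × 0.6:

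- f = 10%: −1.5 points
- f = 20%: −3 points
- f = 50%: −7.5 points

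With stable f and more 'No' answers after surgery, the rule therefore makes improvement look smaller. If f itself differs between visits, the error can go either way.

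**'Yes' pairs.** The note does not cover them. Read literally, the formula averages 'Yes' (0) with its follow-up: 'Not at all' gives (0 + 75)/2 = 37.5, 'A little' 25, 'Somewhat' 12.5 and 'Very' 0. Scored by the follow-up alone, the same pairs give 75, 50, 25 and 0. The SAP does not say which is meant.

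**The case against.** The SAP foresaw the pattern and prespecified one rule for all three pairs on both questionnaires. Letting the more specific answer prevail is a recognisable convention. The item wording is not in the documents, so reading 'No' as symptom-free, and 'No' plus 'Not at all' as consistent, is an interpretation. A printed skip may make the pattern rare. The SAP also refers normalisation to a cited psychometric paper that cannot be checked here. All responses are listed by subject, so affected pairs could be found and rescored later.

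Most of this limits the size of the point and does not remove it. Prespecifying the rule does not explain why an apparently compatible pair should lose 25 points, and a rare pattern is still scored wrongly when it occurs. If the rule comes from the cited paper, the SAP should say so.

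A reader might infer that Appendix B orders subjects to do what the SAP forbids. The text does not go that far. It encourages completion, one box per question, and is silent on skips; the advice to guess is for uncertainty about an answer, not for items that do not apply. It shows only that the pattern can occur.

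A reader might also put the bias in change from baseline at 25 times the pre/post difference in f. That omits the share answering 'No'. With f = 20% at both visits it gives 0, whereas the assumed case above gives −3.

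**Conclusion.** The point holds as a small scoring flaw. Under SAP 6.5.8.9, 'No' plus 'Not at all' scores 75 and 'No' with a blank scores 100. That is 25 points per affected pair, and up to 25 on the domain if all three pairs are affected.

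This rests on reading the two answers as compatible. How often it happens is unknown, so the effect on the mean can only be given as 25 × f × p with assumed values.

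The note is written for Vision Clarity alone. It would be wrong to infer that PROWL as a whole, or the trial's conclusion, is in doubt: the domain is descriptive, and the three primary endpoints, their tests and the sample size do not use it.

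**What to change.** Change the SAP only, in 6.5.8.9, before database lock. SAP section 4 provides for an amended version approved by then.

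- Score the pair 100 when the lead item is 'No' and the follow-up is blank or 'Not at all'.
- Keep the current rule for 'No' with 'A little', 'Somewhat' or 'Very', and report the number of such pairs.
- In the same line, state how a 'Yes' pair is scored: by its follow-up alone, or by another stated rule.

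Leave the Appendix B instruction as it is. Protocol 7.4.1.1 shows that subjects had already been treated by March 2020, and the SAP is written to protocol version 8.0 of November 2020. A new instruction now could give some subjects different directions before and after surgery, which could itself create a pre/post difference in f. Do not query subjects about their answers either; protocol 5.2.3 and 8.5 require completion without direction from clinic staff.

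The cost is a little programming and one added count. No new data are needed, and the rule applies equally to forms already collected.
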